- Fasting glucose, HbA1c, IGF-1, TSH, creatinine, SGPT, urine pregnancy test, HCT, Ghrelin
- DXA scan to evaluate for osteopenia and body composition
- Measurement of bone age for males 18 or 19 years old

Study Visits:

1. Baseline: (n=75: 38 healthy obese women and 37 healthy obese men)

The baseline visit will occur within 8 weeks after the screening visit. The following assessments will be made during the baseline visit days and will occur within a 30-day period.

- Assessment of potential factors affecting BMD: family history of osteoporosis, alcohol, free testosterone, estradiol, exercise (Paffenbarger Physical Activity Questionnaire and Modified Activity Questionnaire (MAQ)), Calcium & Vitamin D Intake (Calcium & Vitamin D Frequency Questionnaire), and food diary log
- Waist circumference, weight, and BMI
- 2-hour GHRH-arginine GH stimulation testing

Partners Human Subjects Research Application Form Version Date: June 1, 2005

- CT
- DXA scan (only if baseline occurs more than 6 weeks after screening visit)
- Xtreme CT
- Head x-ray if subject reports possibility of metal in face or head
- MRI/MRS
- Blood drawn to determine levels of hormones and other chemicals
- Oral glucose tolerance test (OGTT)
- Functional Strength Test

2. Follow-up visits:

The following assessments will be made during the 6 week, 3 month, 4.5 month, 6 month, 9 month, 12 month, 15 month, 18 month and 24 month visits. The 3 week, 9 week, and 4 month visits will be performed during a \pm 2 week interval around the indicated return time to allow for potential scheduling conflicts. The 6 month, 9 month, 12 month, 15 month, 18 month and 24 month visits will be performed during a \pm 1 month interval around the indicated return time. Subjects who drop out or are discontinued from the study after participating for at least 9 months will be asked to come in for a final study visit that will be identical to the 18-month study visit. The follow-up visits involve:

- Medical history, physical examination, weight, waist and hip. Return menses (for women), growth hormone dosing records, and all study medication vials.
- DXA scan (12 month, 18 month, and 24 month visits)
- CT scan (18 month visit)
- Low-dose CT for body composition only (6 month visit)*
- Xtreme CT scan (12 month, 18 month, and 24 month visits)
- MRI/MRS (6 month visit* and 18 month visit)

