- Blood drawn to determine levels of hormones and other chemicals (3 week, 9 week, 4 month, 6 month, 9 month 12 month, 15 month, 18 month and 24 month visits).
- OGTT (6 month, 12 month, and 18 month and 24 month visits)
- Paffenbarger Physical Activity Questionnaire and Calcium & Vitamin D Frequency Questionnaire (6-month, 12-month, 18-month, 24-month visits)
- Functional Strength Test (6-month, 12-month, 18-month and 24-month visits)
- Food diary log (18-month visit)

	-	0	
-			
•			
-			

*discontinued performing starting in August 2017

Study endpoints

Aim 1:

Primary Endpoint: Change in BMD over 18 months in the GH vs placebo group.

Secondary Endpoints:

- 1. Bone microarchitectural parameters
- 2. Bone strength by FEA

Aim 2:

Primary Endpoint: Change in bone marrow fat in the GH vs placebo group. **Secondary Endpoints:**

- 1. Pref-1.
- 1. Bone formation markers P1NP, ucOC.
- 2. Fasting and 2-hour OGTT insulin.
- 3. Inflammatory markers hsCRP, TNF1 receptor, and IL-6.
- 4. Serum lipoproteins.
- 5. 25-OH vitamin D.

Dual-energy X-ray-absorptiometry (DXA): DXA will be used to measure BMD of the AP and lateral spine (L1-L4), distal radius, total hip, femoral neck and total body. Total fat and fat-free mass measurements will also be obtained.

Quantitative computed tomography (QCT): As DXA may overestimate BMD in obesity,¹⁰⁷ we will perform volumetric QCT of L1 and L2 and of the proximal femur (GE LightSpeed Pro CT scanner, GEHealthcare, Waukesha, WI or Somatom Definition, Siemens Healthcare, Forchheim Germany) and low-dose single slice CT of the abdomen and thigh for body composition.

High-resolution CT: High resolution peripheral QCT will be used to measure volumetric density, morphology and microarchitecture at the distal radius and distal tibia (XtremeCT, Scanco Medical AG[®], Bassersdorf, Switzerland). The outcome variables computed by automated analysis will include volumetric BMD (g hydroxyapatite/cm³) for total, trabecular, and cortical regions; cortical thickness (µm) and porosity measures and trabecular number (mm-1), thickness (mm), and separation (mm). HR-pQCT measurements will be performed at the non-dominant wrist and leg in the absence of a history of fracture.

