A number of procedures will be instituted to protect against potential risk involved in this protocol. The potential effects of growth hormone on a fetus are not known and therefore precautions against administration to pregnant patients will be instituted. All patients will have pregnancy tests on admission prior to receiving radiation or study medication. Subjects will also have serial pregnancy tests – one at every study visit – and study participation will be discontinued if a subject becomes pregnant. DXA scans and cross-sectional CT scans will be performed during the length of the protocol. The combined radiation from these procedures is approximately 9% of the amount of radiation to which a person who works with radiation can be exposed each year.

Because of the potential importance of insulin resistance to cardiovascular risk, we will investigate with validated techniques, including oral glucose tolerance test, the effects of GH on insulin resistance in our population. Because glucose tolerance may deteriorate with GH administration, especially acutely, we will not allow patients with DM to participate and we will discontinue study participation if a subject develops fasting plasma glucose >=126 mg/dl or 2-hour post OGTT glucose >= 200 mg/dl while they are taking the study medication (between the baseline visit and the day before the 18 month visit).

A physician will be available at all times during the study by pager to answer any questions a patient might have. The physician will arrange to immediately see every patient with a concern. All efforts will be made to protect the confidentiality rights of the study subjects who will be referred to by code numbers only. Confidentiality of the patients will always be of paramount importance to study investigators. No data on patients will be shared with persons other than those directly involved in the study, except at the documented request of the patient. Samples that are sent to laboratories outside of will be labeled with a non-identifying numeric code.

All adverse events will be reported to the IRB in a timely manner according to the guidelines provided by Partner's Human Subjects Research Committee.

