Describe explicitly the methods for ensuring the safety of subjects. Provide objective criteria for removing a subject from the study, for example, objective criteria for worsening disease/lack of improvement and/or unacceptable adverse events. The inclusion of objective drop criteria is especially important in studies designed with placebo control groups.

Safety assessments

- 1. IGF-I levels:
 - a. Must have IGF-I within or below the lowest 2 quartiles for age and gender
 - b. Measurements at screening, baseline, 6week, 3 month, 4.5 month, 6 month, 9 month, 12 month, 15 month, 18 month and 24 month
 - c. Dose decrease for IGF-I levels above the upper limit of normal
- 2. Glucose: 2 hour 75 g OGTT: baseline, 6, 12, 18 and 24 months. Fasting glucose at screening, 6 week, 3 month, 4.5 month visits.
- 3. Pregnancy testing: screening, baseline, 6 week, and 3, 4.5, 6, 9, 12, 15, 18 and 24 months (Additional testing will be arranged if lengthened menstrual cycle)
- 4. HbA1c: screening, 6 month, 12 month, 18 month and 24 month

Subjects will be discontinued from the study if they develop

- a. Glucose: fasting \geq 126 mg/dl or 2h GTT \geq 200 mg/dl while they are taking the study medication (between the baseline visit and the day before the 18 month visit)
- b. Diabetes: $HbA1c \ge 6.5\%$
- c. Positive pregnancy test
- d. Severe / intolerable side effects of GH
- e. Development of malignancy
- f. Initiation of the following medications: OCPs

FORESEEABLE RISKS AND DISCOMFORTS

Provide a brief description of any foreseeable risks and discomforts to subjects. Include those related to drugs/devices/procedures being studied and/or administered/performed solely for research purposes. In addition, include psychosocial risks, and risks related to privacy and confidentiality. When applicable, describe risks to a developing fetus or nursing infant.

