## Statistical Power and Statistical Analysis

**Statistical power:** For Aim 1, primary endpoint, with an n=75 and 50 completers, we will have >80% chance of detecting a difference in the rate of BMD AP lumbar spine increase of 0.024g/cm^2/y at a 2-sided  $p=0.05$  level. This compares favorably with the rate of BMD AP spine increase of 0.036 g/cm^2/y in a study by Baum *et al.* administering GH for 18 months to hypopituitary subjects with GH deficiency. This was calculated with software developed by co-investigator [REDACTED] for sample size for random slopes models, available in Matlab [REDACTED]. The variance covariance matrix of the random effects,  $\Psi$ , and residual variance,  $\sigma^2$ , were estimated from longitudinal data from Baum *et al.* that had originally been analyzed by [REDACTED]. The variance of the intercept was 0.024, slope 0.000211, covariance 0.00199 and residual variance,  $\sigma^2$ , 0.00092 and an exponential drop-out rate of 0.36/yr, which is greater than we expect. The program uses the fact that the variance covariance matrix for the fixed effects of the model are:  $\mathbf{V(B)} = \{\mathbf{X}'[\sigma^2] + \mathbf{Z\Psi Z}'\}^{-1}\mathbf{X}$ . One incorporates drop outs by replacing  $\mathbf{X}'[\sigma^2] + \mathbf{Z\Psi Z}'\}^{-1}\mathbf{X}$  by a weighted sum for different follow-up times with weights equal to the follow-up probability -- a special case of the general model described in Pinheiro and Bates. For Aim 2, primary endpoint, with 50 completers we can detect 0.81 x SD of the difference in bone marrow fat content over a year; For secondary endpoints: for trabecular thickness (TbTh) and cortical thickness (CoTh), based on our preliminary data in obese men receiving placebo for 6 months in which the standard deviation (SD) of the change in TbTh was 0.0047mm and of CoTh was 0.0015mm, we will be able to detect an annual increase of 0.008mm and 0.012mm, respectively; for FEA we will have a power of 80% at a two-sided  $p=0.05$  significance level, if the true rate of difference in estimated failure load between the treatments is 316 units, based on an assumption that the SD is 570 units, as derived from Boutroy *et al.* With 50 completers, we will have an 80% power at a 2-sided  $p=0.05$  level to see a difference in PINP of 38.6 ng/ml, total abdominal fat of 50.8 cm^2, lean mass of 1.2 kg, vitamin D of 0.025 ng/ml, hsCRP of 0.025 mg/l, and apoB of 18.6 mg/dl per year. These were calculated from our preliminary data administering GH to obese subjects for 6 months. The power for the mediation analyses (see below) depends on the effect size of the treatment on BMD and on the correlation of the secondary endpoint on BMD. We derived a formula using the delta method. With at least 40 subjects we will have an 80% chance of achieving significance at a two-sided  $p=0.05$  level if the effect size is 2 units and the correlation is 0.5. For the 6-month withdrawal period, we will have adequate power to test whether the BMD remains significantly different from placebo at 24 months. We will have 80% power to detect a difference of 0.04 g/cm^2 assuming that there are at least 43 patients still in the study at 18 months (we expect 50).

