
**Data analysis plan:** We will pool data from men and women using a random slopes model; we will consider a model where each patient has a random slope and intercept. The mean intercept and slope may be different for men and women and in each treatment group. The primary analysis is a pooled analysis of treatment effect across gender with weights equaling the frequency of men and women in the sample. A secondary analysis will test for the significance of the treatment-gender interaction on the rate of change of BMD and all other endpoints. For all analyses, an intent-to-treat analysis will be performed. We plan to apply the guidelines developed by the National Research Council regarding missing data. Our primary analysis, the random slopes model, assumes that data is missing at random. We also will conduct two sensitivity analyses. The first assumes that the missing data is a function of the unobserved random effect and the second tests the assumptions in this model under other missingness mechanisms. We will also determine which of the secondary endpoints appears to mediate the treatment effect on an endpoint, such as BMD, microarchitectural parameters, and bone marrow fat by examining the effect of treatment on the potential mediator and of the potential mediator on the endpoint; examples of this will include whether Pref-1 mediates the effects of GH on bone marrow fat or strength, and whether bone marrow fat, body composition variables, inflammatory markers, lipids or vitamin D mediate the effects of GH on bone strength. The effect on one endpoint by a potential mediator is the product of the two effects. The Sobel test will test whether this effect is zero. As there are no known moderators of GH treatment in this population and the population has been purposely selected for osteopenia, we will not control for covariates other than gender in our primary analysis. We will perform exploratory analyses to answer the following: 1. Among an osteopenic population are there covariates

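### Participants who leave before month 9 have no follow-up BMD, so the intent-to-treat slope rests on those who stayed and can overstate the GH effect if early stops are commoner on GH

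*Protocol*

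**What the plan says.** The Aim 1 primary endpoint (Protocol, Study endpoints) is "Change in BMD over 18 months in the GH vs placebo group". The SAP's Data analysis plan states: "For all analyses, an intent-to-treat analysis will be performed". It names the model and its assumption: "Our primary analysis, the random slopes model, assumes that data is missing at random". Two sensitivity analyses follow. "The first assumes that the missing data is a function of the unobserved random effect"; the second examines other missingness mechanisms.

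The protocol's list of removal criteria, under Safety assessments, opens with "Subjects will be discontinued from the study if they develop" and covers glucose, HbA1c, pregnancy, side effects of GH, malignancy and starting oral contraceptives. The section on minimising risk also describes the glucose rule as ending participation in the study. It gives the reason: "Because glucose tolerance may deteriorate with GH administration, especially acutely".

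Under Follow-up visits, DXA after baseline is listed at 12, 18 and 24 months. The only provision for people who leave is this: "Subjects who drop out or are discontinued from the study after participating for at least 9 months will be asked to come in". That exit visit has the content of the month-18 visit. Safety assessments places fasting glucose at 6 weeks, 3 months and 4.5 months, with an OGTT and HbA1c at 6 months.

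**The concern.** An intent-to-treat estimate needs outcome data, or a credible assumption, for everyone randomised. Here a participant who meets a stopping criterion before month 9 leaves the study with a baseline scan and nothing else. Four glucose checks fall in that window, and the protocol itself links worsening glucose to GH, above all early on. Such exits may therefore be more frequent on GH than on placebo.

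Under missing at random, the model in effect assigns these people the mean slope of those in their arm who continued. For someone who has stopped GH, that slope includes a continuing drug benefit that may not exist. The estimate then moves towards the effect in people who remain on GH, while being reported as the effect of assignment to GH.

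**Working it through.** **Inputs.** From the SAP's Statistical power paragraph: "with an n=75 and 50 completers"; slope difference 0.024 g/cm²/y; two-sided 0.05; power above 80%; intercept variance 0.024, slope variance 0.000211, covariance 0.00199, residual variance 0.00092; exponential drop-out 0.36/yr. From the protocol: DXA at 0, 12 and 18 months, with exit scans from month 9. Assumption: 1:1 allocation, which the text available does not state.

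**Step 1: the plan's own power.** Generalised least squares for random slopes, weighted by follow-up probability as the SAP describes, with power = Φ(0.024/SE − 1.96).

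- 0.36/yr with exit scans from month 9: SE 0.00865, power 79.2%.
- 0.36/yr with scans at 0, 12 and 18 months only: SE 0.00903, power 75.7%.
- The rate giving 50 of 75 completers, −ln(50/75)/1.5 = 0.270/yr: 82.5% with exit scans, 80.0% without.

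The stated power is reproduced to within about a point at 0.36/yr with exit scans, and met at 50 completers.

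**Step 2: how many leave before month 9, from any cause.**

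- 75 × (1 − exp(−0.36 × 0.75)) = 17.7, or 24%.
- 75 × (1 − exp(−0.270 × 0.75)) = 13.8, or 18%.

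**Step 3: what their baseline scans contribute.** At 0.36/yr with exit scans, power is 79.2% with the baseline-only records and 78.6% without them. They are in the likelihood but tell it almost nothing about slope.

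**Step 4: possible bias.** Let a share p of the GH arm stop early and keep a fraction r of the benefit, with no corresponding loss on placebo (both assumptions). The model still targets about 0.024. The as-randomised effect is 0.024 × (1 − p(1 − r)), so the overstatement is 1/(1 − p(1 − r)) − 1.

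| p | r = 0 | r = 1/3 |
|---|---|---|
| 5% | 5% | 3% |
| 10% | 11% | 7% |
| 15% | 18% | 11% |
| 24% (all-cause rate, upper bound) | 32% | 19% |

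A simulation with the SAP's variances and r = 0 agrees. For p from 5% to 23.7%, the planned model averaged 0.0235 to 0.0246, while the same model with every participant scanned averaged 0.0188 to 0.0228.

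**Step 5: what off-drug scans would do for power.** At 0.36/yr with exit scans from month 9 and before any dilution:

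- Half of the early leavers return at 12 and 18 months: SE 0.00803, power 84.8%.
- All 75 scanned at both visits: SE 0.00730, power 90.8%.

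With all 75 scanned, a 15% dilution (0.0204) gives 79.8% and a 25% dilution (0.018) gives 69.3%.

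**The case against.** The strongest reply is that the SAP contradicts nothing. It pairs intent-to-treat with a missing-at-random model and sensitivity analyses, commits to published missing-data guidelines, and so expects incomplete data analysed as randomised. It never promises off-treatment BMD. The study is powered on completers, and its question is what 18 months of GH does to bone. This stands in part: the plan is workable as written, and the sensitivity analyses mitigate the problem. They cannot replace BMD that was never collected, however, and they leave the primary estimate as it is. Replacing drop-outs, which the protocol intends, restores numbers but not the outcomes of those who left.

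It is also fair that differential loss is inferred. The protocol says only that glucose tolerance may worsen. It excludes diabetes at entry, lowers the dose for high IGF-1, and gives no stop rate by arm or time. Some glucose stops will come at month 12 or later, where the exit visit applies.

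A reader might infer that early leavers are excluded from the primary analysis. They are not, since baseline BMD keeps them in the likelihood. A reader might also take the 24% row as the expected bias. That row applies all-cause loss, at a rate the SAP calls higher than it expects, to GH-arm stops alone; the documents do not support it as more than an upper bound.

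**Conclusion.** The gap is real. Under the protocol as written, anyone leaving before month 9 has no planned follow-up BMD, so the estimate called intent-to-treat relies on an untestable assumption for perhaps 14 to 18 of 75 participants (all causes, both arms).

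The direction of bias is plausible but not established: if early stops are commoner on GH and the benefit fades after stopping, the effect is overstated. The size is unknown. With 5–15% of the GH arm stopping early, it is about 5–18% with no retained benefit and about 3–11% with a third retained. Those shares and the retained fraction are assumptions, as is the absence of matching loss on placebo. One part of the SAP was not available to check, so a follow-up provision there cannot be ruled out.

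It would go too far to say that treatment-related loss is known to differ by arm, or that the plan breaks its own intent-to-treat rule. This is an inexpensive improvement that should be made, not a fatal flaw.

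**What to change.** Leave every criterion for stopping study drug unchanged. In the protocol, separate stopping study medication from ending study participation. Ask participants who stop drug and still consent to attend the already scheduled 12- and 18-month visits for DXA only, unless scanning is contraindicated (for example, by pregnancy). Include these scans in the primary model in the arm as randomised, and report an on-treatment analysis as a sensitivity analysis.

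The 9-month threshold for the full exit visit need not change. Exit scans for all early leavers at week 6, month 3 or month 6 would move power only from 79.2% to 79.4%, 79.7% or 80.9%, and that visit carries the whole month-18 set of procedures.

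The cost is protocol wording and some return visits, with no new procedure. The downside is a possibly smaller, diluted effect estimate. Before dilution, power at 0.36/yr rises from about 79% to about 85% if half of the early leavers return. The 91% figure needs all 75 scanned, which wording alone cannot secure because some people will withdraw consent. For participants who had already left before this 2019 version, missed scans may be unrecoverable.

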Bone Strength: Finite element (FE) models will be generated and analyzed as published⁹³ using software provided by Scanco Medical AG (Bassersdorf, Switzerland) by converting each voxel to an equally-sized brick element,¹¹¹ resulting in FE models with approximately 2 million elements.

MR spectroscopy: Proton MR Spectroscopy of lumbar vertebral and femoral bone marrow (for lipid content), muscle and liver (for lipid content) will be performed with a 3.0 Tesla MR scanner (Siemens Trio, Siemens Medical Systems, Erlangen, Germany) as previously described by our group.^{97, 105, 106, 114-116}

Functional strength testing: Functional strength of the hand and forearm will be determined. Additionally, functional strength of the lower and upper extremities will also be determined.

Endocrine testing:

- fasting GHRH-arginine stimulation test
- GH
- IGF-1
- Bioactive IGF-1
- P1NP and CTX
- Osteocalcin
- Pref-1
- hsCRP and apoB
- IL-6 and TNF-)-α receptors I and II
- Testosterone
- Estradiol and SHBG
- 75-g oral glucose tolerance test (OGTT)

Partners Human Subjects Research Application Form Version Date: June 1, 2005 • Glucose, insulin, hemoglobin A1c, 25(OH) vit D, 1,25 (OH)₂ vitamin D, ionized calcium, phosphorous, iPTH, total cholesterol, LDL, HDL, and triglycerides

For studies involving treatment or diagnosis, provide information about standard of care at Partners (e.g., BWH, MGH) and indicate how the study procedures differ from standard care. Provide information on available alternative treatments, procedures, or methods of diagnosis.

Understanding the pathophysiology of bone loss in obesity may help identify new treatment targets for this important complication. We have excluded potential study subjects with severe bone loss and will refer them for treatment. Mild bone loss, such as we are studying, is not typically treated in young patients, but rather monitored. We will share BMD results with study participants and their physicians (with participants' permission).

Describe how risks to subjects are minimized, for example, by using procedures which are consistent with sound research design and which do not unnecessarily expose subjects to risk or by using procedures already being performed on the subject for diagnostic or treatment purposes.

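### After month 6 the safety schedule names glucose tests only every six months while participants are on drug, although blood is already drawn at months 9 and 15

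*Protocol*

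**What the plan says.** The glucose stopping rule appears twice in the protocol, in the answer on minimising risk and in the discontinuation list under Safety assessments. It applies "while they are taking the study medication (between the baseline visit and the day before the 18 month visit"). The reason given is "Because glucose tolerance may deteriorate with GH administration, especially acutely". A separate rule discontinues for HbA1c of 6.5% or more and states no time window.

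The tests meant to serve these rules are under Safety assessments:

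- Item 2 names OGTTs at baseline and months 6, 12, 18 and 24, and adds: "Fasting glucose at screening, 6 week, 3 month, 4.5 month visits".
- Item 4 reads: "HbA1c: screening, 6 month, 12 month, 18 month and 24 month".

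The follow-up visit list agrees on the OGTT: "OGTT (6 month, 12 month, and 18 month and 24 month visits").

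Blood is nevertheless taken between these visits: "Blood drawn to determine levels of hormones and other chemicals (3 week, 9 week, 4 month, 6 month, 9 month 12 month, 15 month", and then at months 18 and 24. Safety items 1 and 3 name IGF-I and pregnancy testing at both month 9 and month 15. The Endocrine testing list includes "Glucose, insulin, hemoglobin A1c" but gives no visit times.

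**The concern.** A stopping rule can act only when a test is done. Here the rule covers all 18 months of dosing, but the tests named for it thin out after month 6. The next named test is at month 12. The one after that, at month 18, comes when the rule has already lapsed. A rise in fasting glucose without symptoms, starting soon after month 6 or soon after month 12, could therefore be accompanied by up to about six further months of injections before any named test could show it.

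The participants have a BMI of at least 25. Those with a history of diabetes are excluded, but the listed criteria set no upper limit for glucose short of that. The sponsor itself identifies worsening glucose tolerance as a risk of the drug. At stake is some avoidable dosing in people who already meet the sponsor's own criterion for stopping. The validity of the efficacy result is not in question.

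**Working it through.** The plan states no figure for the interval between tests, so there is none to reproduce. The check sets the named test times against the stopping window.

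**Inputs**
- Named glucose times from baseline to month 18 (Safety assessments, item 2): 0, 6 weeks (about 1.4 months), 3, 4.5, 6, 12, 18. An OGTT is taken to include a fasting sample.
- Named HbA1c times after screening, up to month 18 (item 4): 6, 12, 18.
- Existing draws between these: months 9 and 15 (follow-up visit list; item 1 for IGF-I).
- Visit window: "The 6 month, 9 month, 12 month, 15 month, 18 month and 24 month visits will be performed during a" ±1 month interval.
- Numbers at risk: 50 completers (protocol), or 75 enrolled with exponential drop-out of 0.36 per year (SAP, Statistical power).

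**Gaps between successive named tests (months)**
- Now: 1.4, 1.6, 1.5, 1.5, **6, 6**.
- With months 9 and 15 added, for the fasting limit: 1.4, 1.6, 1.5, 1.5, **3, 3, 3, 3**.

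**Effect of visit windows**
- 6-month gap: shortest 11 − 7 = 4 (or 17 − 13 = 4); longest 13 − 5 = 8 (or 19 − 11 = 8).
- 3-month gap: shortest 8 − 7 = 1; longest 10 − 5 = 5. The other three 3-month gaps give the same range.

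**Participant-months in each six-month gap, both arms**
- With 50 completers: 50 × 6 = 300 in each.
- With drop-out, the number at month t is 75·exp(−0.36·t/12): 62.6 at month 6, 52.3 at month 12, 43.7 at month 18.
- Months 6–12: 75 × 12 × (e^−0.18 − e^−0.36)/0.36 = 344.
- Months 12–18: 75 × 12 × (e^−0.36 − e^−0.54)/0.36 = 287.
- If allocation is 1:1 (assumed; the visible text does not state it), about half of each figure is on GH: 150 and 150, or 172 and 144.

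**Undetected dosing after a persisting fasting rise**
- If onset is spread evenly over a gap (assumed), the mean is half the gap: 6/2 = 3.0 months now, 3/2 = 1.5 months with the added test.
- The share of such rises found at the midpoint, with about three months of the interval left, goes from 0 to 3/6 = 50%.
- Both results follow from placing a test at the midpoint under even onset. They describe the schedule and are not evidence of how many people would benefit.

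**What does not change**
- The 2-hour limit and HbA1c remain tested at months 6 and 12 within the window, so their gaps stay at 6 months.

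**The case against.** The strongest case against is that the schedule is deliberate. The sponsor expects deterioration mainly early, and a participant whose results are unremarkable through month 12 has had five on-drug glucose checks. The documents set no maximum interval between tests, so none is breached. IGF-I is measured at months 9, 12 and 15 with dose reduction above the normal range, which limits over-exposure. Each visit includes a history and examination, and a physician is on call. All of this stands and keeps the severity modest. It does not supply a test for a symptomless rise, and the sponsor's own month-12 OGTT shows that late risk was not taken to be nil.

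A second objection is that glucose may already be run at months 9 and 15. The documents leave this open: the visit list speaks only of hormones and other chemicals, the assay list carries no visit times, and the end of the follow-up list cannot be read. The point is therefore limited to what the safety schedule names.

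Two stronger readings are tempting. A reader might infer that months 12 to 18 are a special blind spot because no in-window test follows month 12. The documents do not support this. Months 6 to 12 have the same nominal gap and the same ceiling of six months' undetected dosing. They also hold more participant-months under the SAP drop-out rate (344 against 287) and lie closer to the early period that the sponsor worries about. A reader might also infer that ending the rule before the month-18 visit is an error. It is not: the rule is tied to taking the drug, and the month-18 test has no dosing left to stop.

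**Conclusion.** The point holds for both late intervals and for the fasting limit. Between months 6 and 18 the safety schedule names one on-drug occasion, month 12, at which the glucose rule can be triggered, while two existing blood draws are not named for glucose. Using them would halve each nominal gap from 6 to 3 months and reduce the longest gap that the visit windows allow from 8 to 5 months.

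The importance is modest. No rate of glucose events is given, so the number of participants affected cannot be estimated. The participant-month figures rest on either 50 completers or the SAP's drop-out rate, which the SAP says is higher than expected. The waiting times rest on even onset and on a rise that persists. The case for change is that it costs little and serves the sponsor's own rule; no requirement in the documents has been broken.

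**What to change.** In Safety assessments, item 2, add fasting glucose at the existing month-9 and month-15 blood draws. If glucose is already run there as part of the Endocrine testing list, name it in item 2 and require the participant to fast. Leave the thresholds, the stopping window and the OGTT schedule as they are.

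The cost is a short amendment, two fasting instructions and two inexpensive assays per participant, with no new visit. At the SAP drop-out rate that is about 75·e^−0.27 = 57 participants at month 9 and 75·e^−0.45 = 48 at month 15; counting the 50 completers alone, it is 50 at each.

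The downside is that a few more participants may meet the existing rule, which names no confirmatory test, so a single value at the limit could end participation before the 18-month endpoint. The final visit requested of those who leave after at least 9 months offsets that loss only in part.
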